10.4.2. Contraception Guidance

Male Subjects:

Male subjects are eligible to participate if they agree to the following from informed consent, during the treatment period and for 90 days after the last dose of study drug:

- Refrain from donating sperm

PLUS, either:

- Be abstinent from heterosexual intercourse as their preferred and usual lifestyle (abstinent on a long term and persistent basis) and agree to remain abstinent

OR

- Must agree to use contraception/barrier as detailed below
 - Agree to use a male condom

Female Subjects:

- A female subject is eligible to participate if she is not pregnant or breastfeeding, and at least one of the following conditions applies:
 - Is not a woman of childbearing potential (WOCBP)

OR

- Is a WOCBP and using a contraceptive method that is highly effective (with a failure rate of < 1% per year), preferably with low user dependency (see table below), at least 28 days prior to Screening, during the intervention period, and for 30 days after the last dose of study drug, and agrees not to donate eggs (ova, oocytes) for the purpose of reproduction during this period. The investigator should evaluate the effectiveness of the contraceptive method in relationship to the first dose of study drug.
- A WOCBP must have negative serum pregnancy test (minimum sensitivity 25 IU/L or equivalent units of human chorionic gonadotropin [HCG]) within 72 hours prior to receiving the first administration of study drug.
- If a urine test cannot be confirmed as negative (e.g., an ambiguous result), a serum pregnancy test is required, and results must be negative. In such cases, the subject must be excluded from participation if the serum pregnancy result is positive.

Contraceptive use by men or women should be consistent with local regulations regarding the use of contraceptive methods for those participating in clinical studies.

Note: Ethinyl estradiol is the primary estrogen used in hormonal contraceptives. The progestin component consists of norethindrone, levonorgestrel, norgestrel, norethindrone acetate, ethynodiol diacetate, norgestimate, desogestrel, and drospirenone. As BLD-2660 is a weak CYP3A4 inducer, exposure to both the estrogen and progestin components in hormonal contraceptives may be decreased, resulting in an increased risk of pregnancy. As such, it is recommended that subjects who are on hormonal contraceptives for birth control should use an

alternate means of contraception (condoms, diaphragms, IUD, other barrier methods, sexual abstinence, etc.) during participation in the study.

10.4.3. Collection of Pregnancy Information

- In the event of a pregnancy, the female subject or partner of a male study subject should be referred to an obstetrician/gynecologist experienced in reproductive toxicity for further evaluation and counseling.
- The Investigator will follow the female subject or partner of a male study subject until completion of the pregnancy
- The Investigator must notify the Sponsor's Medical Monitor of the outcome within 5 days.
- The Investigator will provide this information as a follow-up to the initial report.
- If the outcome of the pregnancy meets the criteria for immediate classification as an SAE (e.g., spontaneous abortion [any congenital anomaly detected in an aborted fetus is to be documented], stillbirth, neonatal death, or congenital anomaly), then the Investigator should report it as such.
- All neonatal deaths that occur within 30 days of birth are to be reported, without regard to causality, as SAEs. In addition, any infant death after 30 days that the Investigator suspects is related to the in-utero exposure to the study drug should also be reported.

10.5. Appendix 5: Cardiac Monitoring Protocol

All troponin elevations and cardiac AEs and SAEs will be reviewed by the DMC.

Subjects with elevated troponins will be questioned regarding occurrence of any cardiac symptoms. The symptoms will be evaluated by a study investigator and a consulting physician independent of the investigator team who will recommend whether any additional studies should be performed. In addition, during the evaluation period:

1. Study drug could be withheld, at the discretion of the investigator
2. Serum troponin, Creatine Kinase-Myocardial Band (CK-MB), myoglobin, comprehensive metabolic panel (including AST) will be obtained and echocardiogram and ECG performed and interpreted
3. Detailed history of potential causes of troponin elevation should be obtained
4. Additional work up will be initiated per the Investigator's discretion and cardiology consultant

If work up is negative, as determined by Investigator and/or Medical Monitor, no further action is required and, if the study drug had been stopped, it may be restarted.

If work up is positive for a cardiac source, the DMC will review and determine whether the study drug should be permanently discontinued and advise on any next steps, if any.

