2.3.1. Risk Assessment

Potential Risk of Clinical Significance	Summary of Data/Rationale for Potential Risk for Study Drug BLD-2660	Mitigation Strategy
Elevated troponin	Transient, asymptomatic mild troponin elevation was observed in 2 healthy volunteers in Phase 1; there were no associated clinical, electrocardiographic or imaging findings and these changes resolved without sequelae despite continued dosing. Biologically, calpain inhibition has not been associated with cardiac toxicity in animal models, and there was no evidence of cardiac toxicity in acute and chronic toxicology studies.	Safety cardiac monitoring protocol (see Section 10.5)

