6.5. Study Drug Compliance

Compliance with study drug will be assessed by the study staff by documenting that at all 6 capsules per dose are administered. Unused capsules that have been dispensed to the subject but not administered should be documented as such in the source documents and CRF. Deviation(s) from the prescribed dosage regimen should be recorded in the eCRF.

A record of the number of BLD-2660 capsules dispensed to and taken by each subject must be maintained and reconciled with study drug and compliance records. Drug start and stop dates, including dates for drug delays will also be recorded in the eCRF.

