where $z_{\alpha/2}$ and z_{β} are the value from a standard normal distribution, π is the proportion of participants randomized to control, $1 - \pi$ is the proportion of participants randomized to active and θ is the standardized effect size we wish to detect. For this study $\alpha = 5\%$, $\beta=10\%$, $\pi=1/3$ and $\theta=0.625$ (i.e., $25/40$).

4. Analysis Sets

For purposes of analysis, the following populations are defined:

Population	Description
Enrolled	All randomized participants
Full Analysis Set (FAS)	All randomized participants who receive at least one dose of study drug. This population will be used for all efficacy analyses
Modified Intent to Treat (MITT)	All randomized participants who receive at least one dose of study drug and one post baseline assessment of the SpO ₂ /FiO ₂ ratio. This population will be used for the primary and secondary endpoints related to improvement in SpO ₂ /FiO ₂ ratio.
Per Protocol Analysis Set (PP)	All randomized participants who receive at least 6 doses of study drug without any major protocol violations that would impact the assessment of the primary efficacy endpoints. This population will be used for efficacy analyses of the primary efficacy endpoints
Safety Analysis Set	All enrolled participants who receive any study drug
PK Analysis Set	All enrolled participants who receive any study drug and have plasma concentration data

5. Statistical Analyses

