5.4. Participant Disposition

A clear accounting of disposition, including the numbers and percentages of participants screened, randomized, completed treatment and completed post treatment follow-up and completed post study follow-up, will be reported overall and by treatment group. In addition, the primary reasons for early discontinuation of study intervention during the treatment period and early study discontinuation will be reported overall and by treatment group. A graphical representation of participant disposition, by treatment group, will be produced using a CONSORT flow diagram.

A summary of the number of participants included in each analysis set (i.e., FAS, MITT, PP, Safety, PK) will be provided overall and by treatment group. Participants could be excluded from an analysis set for more than one reason. All participants excluded from an analysis set will be listed with the reason(s) for exclusion.

A tabular summary of all major protocol violations will be provided by treatment group and overall. Major protocol violations will be classified as follows:

- Violations of inclusion and exclusion criteria
- Receiving the wrong study intervention
- Non-compliance with study intervention. A participant is defined as non-compliant if the participant took < 80% of the study intervention.
- Taking a prohibited medication
- Other

As participants can report multiple protocol violations, they will be included for each observed violation (i.e., these categories will not be mutually exclusive).

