5.8.1. Extent of Exposure

Duration of study drug exposure, defined as the number of days between the date of first dose following randomization and the date of the last dose, will be summarized by treatment group.

Duration will be calculated as date of last dose – date of first dose + 1.

In addition, the number and proportion of participants with study drug exposure of 0-3, 4, 5, 6, 7 and 8-10 days will be summarized by treatment group

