5.9.7. Compliance

Compliance will be calculated and summarized by treatment group. Compliance will be calculated as $100 \times (\text{total number of capsules taken} / \text{total number of capsules expected to be taken})$. The total number of capsules taken is recorded on the eCRF. The number of expected capsules taken will be calculated as the duration of dosing (last dose date minus first dose date, plus 1) multiplied by 12. For example, if a participant is dosed for 10 days the expected number of capsules taken is 120.

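### A troponin hold and restart permitted by Appendix 5, if it exceeds 20% of the dosing span, scores below 80% compliance, so a participant who followed the protocol can be lost from the per-protocol set

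*Protocol*

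**What the plan says.** **Hold and restart.** Protocol Section 10.5 covers the work-up of an elevated troponin: "Study drug could be withheld, at the discretion of the investigator". After a negative work-up, "if the study drug had been stopped, it may be restarted". No maximum length of hold is given. Troponin elevation is the only row in the risk table (Protocol Section 2.3.1).

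**Compliance.** SAP Section 5.9.7 divides capsules taken by capsules expected. The expected number is "calculated as the duration of dosing (last dose date minus first dose date, plus 1) multiplied by 12". Held days are not subtracted.

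**Major violation.** SAP Section 5.4 lists non-compliance among the major protocol violations: "A participant is defined as non-compliant if the participant took < 80% of the study intervention". It says nothing about withholding that the protocol allows.

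**Per-protocol (PP) set.** SAP Section 4 requires at least 6 doses, "without any major protocol violations that would impact the assessment of the primary efficacy endpoints". It does not say which major violations meet that condition.

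**Use of the sets.** Both primary analyses use the full analysis set (FAS; SAP Section 5.5.2). PP is the only sensitivity analysis listed for time to clinical improvement, and one of two listed for SpO2/FiO2 (SAP Section 5.5.3).

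**Exposure.** In SAP Section 5.8.1, "Duration will be calculated as date of last dose" less the first-dose date, plus 1.

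**Data available.** Protocol Section 6.5: "Drug start and stop dates, including dates for drug delays will also be recorded in the eCRF".

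**The concern.** The clinical rule and the analysis rule do not meet. A participant can be managed exactly as Appendix 5 provides, take most of the course, and still be tabulated as a major protocol violator because the formula expects capsules on days when the drug was withheld. A participant who stops permanently is not penalised, because the last-dose date shortens the denominator.

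The event that triggers the hold is the one risk the protocol attributes to the drug. If BLD-2660 raises troponin, long holds will be more frequent on active treatment. Removal from PP would then be a consequence of treatment and would fall unevenly on the arms. A PP analysis offered as a check on the primary result would carry a selection effect of its own. The exposure table would also show uninterrupted dosing for the participants in whom a cardiac signal interrupted it.

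**Working it through.** **Inputs.** 6 capsules per dose and two doses a day, so 12 capsules a day (Protocol Table 3); denominator from SAP 5.9.7; cut at under 80% (SAP 5.4); PP minimum of 6 doses (SAP Section 4). Assumption throughout: two doses are due on every day of the span, and no dose is missed except those held.

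**Plan's own figure.** A 10-day span gives 12 × 10 = 120 expected capsules, as SAP 5.9.7 states.

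**Formula.** With a span of D days and m held doses inside it,

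compliance = 100 × (12D − 6m) / (12D) = 100 × (1 − m/(2D)).

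This is below 80% when m/(2D) exceeds 20%, that is, when m > 0.4D.

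**Ten-day course (120 expected).**

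| Hold | Capsules taken | Compliance | Under 80%? |
|---|---|---|---|
| 1 day (2 doses) | 108 | 90.0% | no |
| 2 days (4 doses) | 96 | 80.0% | no |
| 2.5 days (5 doses) | 90 | 75.0% | yes |
| 3 days (6 doses) | 84 | 70.0% | yes |
| 5 days (10 doses) | 60 | 50.0% | yes |

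**Shortest failing hold, by length of course.**

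| Span (days) | Held doses | Compliance | Doses taken |
|---|---|---|---|
| 4 | 2 | 75.0% | 6 |
| 5 | 3 | 70.0% | 7 |
| 6 | 3 | 75.0% | 9 |
| 7 | 3 | 78.6% | 11 |
| 8 | 4 | 75.0% | 12 |
| 9 | 4 | 77.8% | 14 |
| 10 | 5 | 75.0% | 15 |

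Every row meets the 6-dose minimum, so only the compliance rule could exclude these participants. Courses end at hospital discharge if that comes before Day 10, so the shorter spans will occur.

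**Two participants compared.**

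- Held on Days 4–6, resumes on Days 7–10: 7 dosing days, 14 doses, 84 capsules. 84/120 = 70%, a major violation.
- Stops for good after Day 3: 6 doses, 36 capsules. Expected 12 × 3 = 36, so 100%. The 6-dose minimum is met and there is no compliance violation.

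**Exposure.** For the first participant SAP 5.8.1 gives 10 − 1 + 1 = 10 days, against 7 days on which drug was taken. The participant falls in the 8–10 day category rather than the 7-day one.

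**With held doses removed from the denominator.** The 3-day hold scores 84/(120 − 36) = 84/84 = 100%, and the 2.5-day hold scores 90/90 = 100%. The early stopper stays at 100% and is governed, as now, by the 6-dose rule.

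**The case against.** **Neither step is automatic.** A reader might infer that any permitted hold is scored as non-compliance and that the participant then drops out of PP. The documents do not support that. Holds of up to 20% of the span pass, and exactly 2 days in 10 scores 80.0% against a cut of under 80%. PP exclusion also requires that the violation would affect assessment of the primary endpoints, which leaves room to keep the participant. This objection stands and limits the point. It does not remove it, because the SAP gives no criterion for that judgement, and the label of major violator applies whichever way the judgement goes.

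**Section 5.4 does not cite the 5.9.7 formula.** True, but it is the only compliance formula in the SAP. A fixed denominator of 120 would still give the 3-day hold 84/120 = 70%. It would also make a participant discharged after 7 fully dosed days non-compliant (84/120 = 70%), which is hardly intended.

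**Someone who missed 30% of doses was under-dosed, permitted or not.** This is the best argument for leaving the rule alone. It fails on the SAP's own terms. The SAP sets its exposure minimum for PP at 6 doses, and the held participant took 14. Its compliance measure already ignores total exposure, since it gives 100% to a 6-dose course. What stands is that exempting holds admits participants with fewer doses: a 5-day hold in 10 days moves from 50% to 100% with 10 doses taken.

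**The exposure definition is openly a calendar span, and compliance shows the shortfall.** In part. Compliance is summarised by arm, so missed capsules do appear, but permitted holds are not separated from other missed doses.

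**Long holds may be rare.** Possibly. The risk table reports transient, mild elevations in 2 healthy volunteers that resolved while dosing continued, and the exclusion criteria remove participants with a history of ischemic heart disease. The documents give no rate for this population.

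**Conclusion.** The point holds as a gap between the protocol's hold rule and the SAP's compliance rule. A hold and restart allowed by Appendix 5 that exceeds 20% of the dosing span is scored below 80% and listed as a major violation. It can lead to exclusion from PP even though the participant followed the protocol and exceeded the 6-dose minimum. The thresholds rest on two assumptions: no other dose is missed, and the 80% rule uses the 5.9.7 denominator.

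The reach is limited to the violation table, the PP sensitivity analyses of the two primary endpoints, and the exposure summary. A reader might infer that the primary results are at risk. They are not: both use the FAS, which has no compliance condition, and trial success rests on the two primary hypotheses.

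A reader might also want a figure for the bias in the PP hazard ratio. The documents give no hold rate, no hold length and no link between holds and recovery, so none can be derived. If holds are more frequent on active drug, removal from PP would be treatment-related, but its size is unknown.

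**What to change.** - **SAP 5.9.7:** remove doses withheld under Appendix 5 from the expected capsules, using the delay dates recorded in the eCRF.
- **SAP 5.4:** state that withholding permitted by the protocol is neither non-compliance nor a major violation. The existing 6-dose rule in SAP Section 4 remains the PP exposure minimum.
- **SAP 5.8.1:** report duration of exposure both with and without held days, by arm.

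The cost is a few sentences and a small programming change on data already collected. The downside is that PP will include some participants who took fewer doses. The wording should be settled before results by arm are seen, since SAP 5.10 plans an interim analysis for the sponsor's Phase 3 planning ahead of database lock. No change to the clinical hold rule is proposed.

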10.6. Appendix 6: Abbreviations

Abbreviation Term	Description
ACE-2	Angiotensin-converting enzyme 2
AE	Adverse event
ALT	Alanine aminotransferase
APACHE	Acute physiology and chronic health evaluation
ARDS	Acute respiratory distress syndrome
AST	Aspartate aminotransferase
BCRP	Breast cancer resistance protein
BID	Twice per day
BUN	Blood urea nitrogen
CAPN	Small molecule inhibitor of calpain
CFR	Case fatality rate
CIOMS	Council for International Organizations of Medical Sciences
CMH	Cochran–Mantel–Haenszel
COVID-19	Coronavirus disease 2019
CRP	C-reactive protein
CRRT	Continuous renal replacement technique
CRS	Cytokine release syndrome
CT	Computed tomography
CTCAE	Common terminology criteria for adverse events
CYP	Cytochrome P450
ECG	Electrocardiogram
ECMO	Extracorporeal membrane oxygenation
eCRF	Electronic case report form
EOS	End of Study
EOT	End of Treatment
ET	Early termination
EUA	Emergency use authorization
FAS	Full analysis set

Abbreviation Term	Description
FiO ₂	Fraction of inspired oxygen
FVC	Forced vital capacity
GCP	Good Clinical Practice
GGT	Gamma-glutamyl transferase
GLP	Good Laboratory Practice
HC	Hormonal contraceptives
Hgb	Hemoglobin
HIPAA	Health Insurance Portability and Accountability Act
HIV	Human Immunodeficiency Virus
hsCRP	high sensitivity C-reactive protein
IB	Investigator's brochure
ICF	Informed consent form
IEC	Independent Ethics Committees
INR	International normalized ratio
IPF	Idiopathic pulmonary fibrosis
IRT	Interactive Response Technology
ITT	Intent-treat Set
IUD	Intrauterine device
JAKi	Janus kinase inhibitor
LAM	Lactational amenorrhoea method
LDH	Lactate dehydrogenase
LS	Least square
MAD	Multiple ascending dose
MedDRA	Medical Dictionary for Regulatory Activities
MITT	Modified intent-to-treat sect
MMRM	Mixed measures repeated model
NEWS	National Early Warning Score
NGT	Naso-gastric tube
NOAEL	No observed adverse effects level

Abbreviation Term	Description
NSAID	Non-steroidal anti-inflammatory drug
PaO ₂	Partial pressure of oxygen
PCR	Polymerase chain reaction
PK	Pharmacokinetics
PO	Oral
PP	Per protocol
PPAR	peroxisome proliferator-activated receptor
RBC	Red blood cell
SAD	Single ascending dose
SAE	Serious adverse events
SAP	Statistical analysis plan
SARS-CoV-2	Severe Acute Respiratory Syndrome Coronavirus 2
siRNA	Small interfering RNA
SoA	Schedule of Activities
SOC	Standard of care
SpO ₂	Peripheral capillary oxygen saturation
SSNRI	Selective serotonin and norepinephrine reuptake inhibitor
SUSAR	Suspected unexpected serious adverse reactions
TB	Tuberculosis
TEAE	Treatment emergent adverse event
ULN	Upper limit of normal
WBC	White blood cell count
WOCBP	Women of childbearing potential

10.7. Appendix 7: Protocol Amendment History

Prior Amendments

Blade has introduced the following modifications to Protocol Version 2.0. These changes are presented in order of appearance:

Amendment 1, 23 April 2020

Overall Rationale for the Amendment:

Section # and Name	Description of Change	Brief Rationale
1.1 Synopsis 3.0 Objectives and endpoints	
 Reorganize objectives and endpoints For oxygenation endpoints, added definition for medically fit for removal of oxygen Changed mortality rate to be a secondary endpoint Added Day 28 to relevant endpoints 	
 Per FDA request
1.1 Synopsis 1.2 Schedule of Activities 4.0 Study Design 8.3.1 Time Period and Frequency of Collection of AEs	
 Extended the study follow-up to Day 28 Added 60 days post-study to collect mortality, safety data and forced vital capacity 	
 Per FDA request
5.1.1 Inclusion Criteria	
 Added oxygen requirements inclusion criteria 	
 Per FDA request
5.1.2 Exclusion Criteria	
 Modified supplement oxygen exclusion criteria Added cross reference to the Concomitant Medication section of the protocol Clarified excluded COVID therapies prior to study entry 	
 Based on Investigator's input For clarity and safety measure
6.6 Concomitant Therapy	
 Updated restricted medications section to include azithromycin Clarified to consult with Sponsor's Medical Monitor prior to prescribing chloroquine, hydroxychloroquine and azithromycin Expanded section to include medications affected by potential interactions with BLD-2660 	
 Per FDA request Safety precaution

Section # and Name	Description of Change	Brief Rationale
1.2 Schedule of Activities 8.1.2 Oxygenation Measures	
 Clarified procedures for collecting oxygen saturation 	
 Per Investigator feedback
1.2 Schedule of Activities 8.1.4 Clinical Status Ordinal Score	
 Changed to 6-point ordinal scale by collapsing 'not hospitalized' into 1 category 	
 Per FDA request
8.1.6 Hospital Discharge Readiness Criteria	
 Clarified normal oxygen saturation criteria Clarified oxygen supplementation status will be captured in the database 	
 Per FDA request
8.2.1 Physical examinations	
 Clarified text 	
 For clarity
1.2 Schedule of Activities 8.4 Pharmacokinetics (PK)	
 Clarified that PK samples will also be collected after first naso-gastric tube (NGT) is inserted 	
 To allow characterization of BLD-2660 using NGT route of administration
1.2 Schedule of Activities	
 Update visit window Remove biomarker blood sampling at screening as well as INR, urinalysis and chest x-ray/CT on Day 21 Add overall survival check Other updates as reflected above (e.g., adding Day 28) 	
 To update per changes to protocol and to ensure consistency throughout protocol
9 Statistical Consideration	
 Added azithromycin use to efficacy analyses Updated to 6-point ordinal scale Updated to reflect Day 28 as EOS Revised interim analysis to include efficacy boundaries and sample size re-estimation when 50% of subjects completed the study 	
 Per FDA request
General	
 Corrected typos, formatting, style Aligned changes across protocol Updated Abbreviation (Appendix 6) 	
 For clarity and readability

